5.6.3 Laboratory Values

Laboratory results will be summarized using Système International (SI) units, as appropriate. Laboratory values that are non-missing and reported as 'below the detectable limit' of an assay will be replaced by half the detectable limit in the summary tables. For all quantitative parameters listed in the protocol Section 9.5.1.4.5, the actual value and the change from Baseline to each postbaseline visit and to the end of treatment (defined as the last on-treatment value, including off treatment assessment) will be summarized by visit using descriptive statistics. Qualitative parameters listed in the protocol Section 9.5.1.4.5 will be summarized using frequencies (number and percentage of subjects), and changes from Baseline to each postbaseline visit and to end of treatment will be reported using shift tables. Percentages will be based on the number of subjects with both non-missing baseline and relevant postbaseline results.

Laboratory parameters will be categorized according to CTCAE, and shifts from baseline CTCAE grades to the worst postbaseline grades will be assessed.

Laboratory test results will be assigned a low/normal/high (LNH) classification according to whether the value is below (L), within (N), or above (H) the laboratory parameter's reference range. The results of LNH classification will be provided in a subject data listing.

The number (percentage) of subjects with postbaseline values worsened from Baseline (with at least 1 CTCAE grade increase) will be presented. Likewise, subjects with postbaseline values of CTCAE Grades 3 or 4 worsened from Baseline will also be summarized. When displaying the summary, each subject will be counted once in the laboratory parameter high and in the laboratory parameter low categories, as applicable.

Laboratory tests such as **CCI**

may be conducted in central laboratories in lieu of local labs for certain parameters due to site capability. In these situations, results from central lab may be combined with those from local lab for the same parameter in the analyses if applicable.

5.6.4 Vital Signs

Descriptive statistics for vital signs parameters (ie, systolic and diastolic blood pressure, pulse, respiratory rate, temperature, weight) and changes from Baseline will be presented by visit.

A subject data listing of vital signs will be provided.

5.6.5 Electrocardiograms

Descriptive statistics for ECG parameters including heart rate, PR interval, QT interval, QTc Bazett (QTcB) interval, QTc Fridericia (QTcF) interval, and RR interval, and changes from Baseline will be presented by visit.

Shift tables will present the worst postbaseline changes from Baseline in ECG interpretation (categorized as normal; abnormal, not clinically significant; and abnormal, clinically significant) to end of treatment.

A subject data listing of ECG will be provided.

In addition, the number (percentage) of subjects with at least 1 postbaseline abnormal ECG result in QTc Fridericia (QTcF) during the treatment period will be summarized. Clinically abnormal ECG results in QTcF will be categorized as follows:

Absolute QTcF interval prolongation:

- QTcF interval >450 ms
- QTcF interval >480 ms
- QTcF interval >500 ms

Change from Baseline in QTcF interval:

- QTcF interval increases from Baseline >30 ms
- QTcF interval increases from Baseline >60 ms

5.6.6 Other Safety Analyses

Descriptive summary statistics for LVEF assessed on echocardiograms or MUGA scans and changes from baseline will be calculated. A subject data listing of LVEF will be provided.

Shift table for ECOG PS will present changes from baseline classification to worst postbaseline classification. A subject data listing of ECOG PS will be provided.

CCI

A large rectangular area of the page is completely blacked out, indicating that the content has been redacted. This redaction covers the majority of the page below the CCI header, from approximately y=572 to y=850.

CCI

5.7 Other Analyses

Not applicable.

5.8 Exploratory Analyses

Exploratory analyses may be conducted as appropriate. Any exploratory analyses that are performed will be appropriately titled and labeled as exploratory and will be clearly distinguished from planned analyses when results are reported in the CSR.

5.9 Extension Phase Analyses

The Extension Phase data in disposition, exposure and key safety will be summarized in the same manner as described in [Section 5](#) at the study closeout, if deemed appropriate. The results will be provided in a separate CSR addendum.

6 INTERIM ANALYSES

No formal interim analyses requiring database lock are planned. The interim futility data review using a snapshot of the database will be performed by the sponsor for each tumor cohort for consideration of potential cohort expansion in the Phase 2 doublet treatment cohorts. An interim futility data review will be conducted when the initial 15 subjects are enrolled in each tumor cohort and required tumor responses assessed by RECIST 1.1 by the investigator are met or sufficient follow-up are reached. Details of the interim futility data review is described in details in Section 9.7.3 of the study protocol.

7 CHANGES IN THE PLANNED ANALYSES

CCI

8 DEFINITIONS AND CONVENTIONS FOR DATA HANDLING

8.1 General Data Handling

Baseline

The baseline value is defined as the last non-missing value reported before first dosing.

Change from Baseline, Percent Change from Baseline

Change from Baseline is defined as post-baseline value minus baseline value.

Percent change from Baseline is defined as follows:

$$\% \text{ Change from baseline} = (\text{Change from baseline}/\text{Baseline}) * 100\%$$

The following factors will convert days to months or years:

$$1 \text{ month} = 30.4375 \text{ days}$$

$$1 \text{ year} = 365.25 \text{ days.}$$

Time (years) from first diagnosis to first dose is:

$$(\text{Date of first dose} - \text{Date of first diagnosis})/365.25.$$

Handling of Missing Data

No imputation will be performed for missing data.

Handling of Missing Dates

The following imputation algorithm will be used for partial or missing dates:

Date of Death (only for subjects that died)

- If only the day of the month is missing, the first of the month will be used to replace the missing day
- If both the day and the month are missing, "January 01" will be used to replace the missing information*
- If a date is completely missing, death date will be imputed as the last known alive date + 1 day

* The imputed death date will be compared with the last known alive date (date of censoring for survival). The maximum date (of the imputed death date, date of censoring for survival + 1) will be considered as the date of death.

Start Date of Subsequent Anticancer Therapy

- If only the day of the month is missing, the subsequent therapy will be assumed to start on the first of the month if this day is later than the last dosing date of study treatment. Otherwise, the subsequent therapy will be assumed to start on the next day of the last dosing date of study treatment

- If both the day and the month are missing, the subsequent therapy will be assumed to start on the "January 01" of the given year if this day is latter than the last dosing date of study treatment. Otherwise, the subsequent therapy will be assumed to start on the next day of the last dosing date of study treatment
- If a date is completely missing, it will be considered as missing

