5.4.2 Secondary Efficacy Analyses

BOR per RECIST 1.1 for Phase 1b part will be summarized in the same manner as described above.

Waterfall plots for maximum tumor shrinkage (ie, postbaseline nadir) in sum of diameters of target lesions will be provided.

DOR will be calculated for subjects whose BOR is confirmed CR or PR. It will be estimated and plotted over time using Kaplan-Meier method if necessary. Median and quartiles of DOR will be provided, alongside the 95% CIs. Range (minimum to maximum) of DOR will also be presented with the censored indicator '+' if applicable. The probability of DOR with its 95% CI at selected duration timepoints will be provided. The 95% CIs for the probability of DOR will be calculated. Censoring rules for DOR are the same as those of PFS ([Table 2](#)). Subjects who show a confirmed CR or PR and without disease progression or death will be censored at the time of the last tumor assessment. The summary of subjects with event/censor along with the reason for censor will also be provided.

DCR and CBR will also be calculated. Estimate of DCR and the corresponding Clopper-Pearson 2-sided 95% CI will be presented. CBR will be calculated for subjects whose BOR

is SD. Estimate of CBR and the corresponding Clopper-Pearson 2-sided 95% CI will be presented.

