5.4.3 Other Efficacy Analyses

OS is defined as the time from the date of first dose to the date of death. All events of death will be included, regardless of whether the event happened while the subject was still taking study drug, or after the subject discontinued study drug. OS will be estimated and plotted over time using the Kaplan-Meier method. Median and quartiles will be provided, alongside 95% CIs. Range (minimum to maximum) of OS will also be presented with the censored indicator '+' if applicable. The probability of OS with its 95% CI at selected timepoints will be provided. Subjects who are lost to follow-up or withdrew consent will be censored at the last known alive date, or the data cutoff date, whichever occurs first. Subjects who remained alive will be censored at the data cutoff date. The summary of subjects with event/censor along with the reason for censor will also be provided.

PFS is defined as time from the date of first dose to the date of the first documentation of disease progression or death, whichever occurs first. PFS will be summarized in the same manner as OS. Subjects without PD or death will be censored at the time of the last tumor assessment. Three-month, 6-month, 9-month, and 12-month PFS rate will be estimated using the Kaplan-Meier method and corresponding 95% CIs will be provided.

Censoring rules for PFS are given in Table 2 below.

Table 2 Censoring Rules for PFS			
No.	Situation	Date of Progression or Censoring	Outcome
1	No baseline or no postbaseline adequate tumor assessments ^a	Date of first dose	Censored
2	Death without disease progression or any new anticancer therapy	Date of death	Progressed
3	Progression documented between scheduled visits, on or prior to new anticancer therapy	Date of the first radiological PD assessment	Progressed
4	Death between adequate assessments (Death before next scheduled assessment or after exactly one missing assessment)	Date of death	Progressed
5	New anticancer treatment started	Date of last adequate radiological tumor assessment ^a prior to or on the date of new anticancer treatment	Censored
6	Death or progression after more than one consecutive missed tumor assessment ^b	Date of last adequate radiological tumor assessment ^a before missed tumor assessment	Censored
7	No progression	Date of last adequate radiological tumor assessment ^a prior to or on the date of data cut-off	Censored

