CR = complete response, PD = progressive disease, PFS = progression-free survival, PR = partial response, SD = stable disease.

a. Adequate tumor assessment is radiological assessment of CR, PR, SD, non-CR/non-PD, or PD as determined by investigators at regular interval as defined in the protocol. Any tumor assessments after new anticancer treatment starts will be removed in the definition of PFS.

b. More than 1 consecutive missed tumor assessment is defined as if the duration between the last adequate radiological tumor assessment and PD or death is longer than 97 days [$=((6+1) \times 2 \times 7) - 1$] for subjects on the every 6 weeks scanning schedule in this study; longer than ($>$) 139 days [$=((9+1) \times 2 \times 7) - 1$] for subjects on every 9 weeks tumor assessment schedule after **CCI** in this study

For subjects moving from one schedule to another:

Missed **CCI** and Week 33 assessments: ($>$)118 days [$=((6+1) + (9+1)) \times 7 - 1$]

The priority of the censoring rules is as follows:

If the subject had PD (No. 3) or death (No. 2, No. 4) prior to or on the date of data cut-off, the following sequence will be applied:

- If the No. 1 is applicable, the date of first dose will be used (censored). However, if the subject died (No. 2, No. 4) within 97 days (14 weeks -1 day) after the first dose and did not meet No. 5, the date of death will be the PFS event date (not censored).
- If the No. 5 before PD or death, and/or No. 6 are applicable, the earliest date of censoring will be used (censored).
- Otherwise, the earliest date of progression (No. 2, No. 3, No. 4) will be the PFS event date (not censored).

If the subject had neither PD (No. 3) nor death (No. 2, No. 4) prior to or on the date of data cut-off, the earliest date of censoring (No. 1, No. 5, No. 6, No. 7) will be used (censored), if the subject met multiple situations.

Censoring rules for OS are provided in Table 3 below.

Table 3 Censoring Rules for OS

No.	Situation	Date of Death or Censoring	Outcome
1	Death before or on data cut-off	Date of death	Death
2	Death after data cut-off	Date of data cut-off	Censored
3	Alive at data cut-off	Date of data cut-off	Censored
4	Lost to follow-up or withdrawal of consent before data cut-off	Date last known to be alive	Censored

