8.2 Efficacy Data Handling

Handling of missing data for tumor assessment result

For the calculation of ORR, DCR and CBR, subjects with missing response status (subjects who do not have adequate postbaseline tumor assessments result) will not be included in numerator, but included in denominator.

Data of tumor assessment result after documented PD or discontinuation from treatment

For the analysis of tumor assessment relevant efficacy endpoints, tumor assessment results after PD or last observation visit (for non-PD subjects) are excluded from the analyses, but included in subject data listing.

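### Does imputing partial start dates of subsequent anticancer therapy to the earliest possible date wrongly turn observed progressions into censoring?

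*SAP*

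**What the plan says.** Section 8.1 gives three cases for the start of subsequent anticancer therapy.

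- Day missing: the rule reads "the subsequent therapy will be assumed to start on the first of the month if this day is later than the last dosing date", and if it is not later, the day after last dose is used.
- Day and month missing: 1 January "of the given year if this day is latter than the last dosing date of study treatment"; failing that, again the day after last dose.
- Wholly missing: left missing.

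The date feeds Table 2 in section 5.4.3. Row 3 counts as an event "Progression documented between scheduled visits, on or prior to new anticancer therapy". Row 5 censors at the last adequate scan "prior to or on the date of new anticancer treatment". Footnote a adds: "Any tumor assessments after new anticancer treatment starts will be removed in the definition of PFS". The priority list lets row 5 override a progression that comes after the new therapy. Section 5.4.2 extends this to duration of response: "Censoring rules for DOR are the same as those of PFS".

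**The concern.** The last dosing date is the only observed date that the imputed start is compared with. Provided therapy began after last dose, the imputed start can equal or precede the true one but never follow it. The rule can thus move a progression from event to censored, never the other way, so its errors do not cancel. Where therapy really followed progression, a made-up date overrides an observed event, and Kaplan-Meier PFS and DOR tend to be too long.

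The same section checks an imputed death date against the date last known alive, so a check against progression looks like an omission. DOR is a secondary endpoint estimated in responders only, where one or two reclassified subjects could move the estimate.

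**Working it through.** **1. The mechanism exists.** Assumed dates: stable-disease scan 6 April, last dose 10 April, progression scan 18 May, therapy begun 25 May.

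- Recorded as May: 1 May is later than 10 April, so the imputed start is 1 May.
- Recorded as year only: 1 January is not later than 10 April, so the imputed start is 11 April.
- Either date precedes 18 May, so row 5 censors on 6 April and the event is lost.
- Row 6 plays no part: 6 April to 18 May is 42 days, below the limit of ((6+1) × 2 × 7) − 1 = 97.

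**2. The same record can be handled correctly.** Change one fact: therapy began on 4 May, still recorded as May. The imputed start is again 1 May and the subject is again censored on 6 April. That is what row 5 requires, because therapy came before the progression. The database looks identical in both cases, so no imputation rule can tell them apart.

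**3. Who can be affected.** The event is lost only if the imputed start precedes progression. The imputed start is at least last dose + 1 day, so progression must come at least 2 days after last dose. With progression 0 or 1 day after last dose, the loss is 0%. Progression documented by the end of dosing is safe.

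**4. Error of each rule.** The alternative considered sets the imputed start no earlier than progression whenever progression falls in the recorded month or year. Progression was placed on each of 1,461 consecutive days (four calendar years); the gaps between progression and therapy are assumptions. A is the share of events that the current rule loses when therapy truly followed progression. B is the share of false events under the alternative when therapy truly preceded it.

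| Gap (days) | A, day missing | B, day missing | A, year only | B, year only |
|---|---|---|---|---|
| 7 | 0.737 | 0.770 | 0.978 | 0.981 |
| 14 | 0.507 | 0.540 | 0.959 | 0.962 |
| 21 | 0.277 | 0.310 | 0.940 | 0.943 |
| Mean of the three | 0.507 | 0.540 | 0.959 | 0.962 |

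For A with the day missing, the loss falls to 0.049 at 28 days and 0 from 30 days. With year only it is still 0.882 at 42 days. The current rule makes no error when therapy came first, and the alternative makes none when therapy came second.

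**5. Break-even.** Let p be the share of such records in which therapy followed progression. The current rule errs in p × A and the alternative in (1 − p) × B. They are equal at p = B / (A + B).

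- Day missing, gaps 7, 14 and 21 days: 0.540 / (0.507 + 0.540) = 0.52.
- Day missing, all gaps from 7 to 42 days on both sides: 0.262 / (0.240 + 0.262) = 0.52.
- Year only, gaps 7, 14 and 21 days: 0.962 / (0.959 + 0.962) = 0.50.

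Unequal windows move the answer. Taking 7 to 42 days after progression but only 7, 14 and 21 days before it gives 0.540 / (0.240 + 0.540) = 0.69 with the day missing. The break-even point thus depends on the assumed gaps, and the SAP supplies neither the gaps nor p.

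**6. The comparison with the death date.** The check against the date last known alive removes an impossible order of events: death before a date on which the subject was alive. The last-dose bound plays a similar part for subsequent therapy by keeping its imputed start after study treatment. Progression may truly come before or after new therapy, so there is no impossible order to remove.

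**The case for a change.** The strongest counter-argument is that new therapy is often given because of progression. If so, p could lie well above one half, and the alternative would misclassify fewer records. As a matter of logic this stands. But progression found by the day after last dose already survives imputation. What remains are subjects whose progression was documented at least two days after dosing ended, and for them the order of progression and new therapy is much less clear. The alternative also makes the imputed therapy date depend on the outcome date.

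A milder request would keep the rule and add a sensitivity run and a listing of subjects whose outcome rests on an imputed start. That would be informative, but it is an optional addition for an effect of unknown and probably small size. Sections 5.4.2 and 5.4.3 already call for events and censorings to be summarised with the reason for censoring. Censoring at new therapy will therefore be visible, although not which dates were imputed.

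Section 8.2 has a paragraph headed "Data of tumor assessment result after documented PD or discontinuation from treatment", which drops scans after a last observation visit that it does not define. If that means the last on-treatment visit, off-treatment progression scans are excluded whatever start date is imputed. That wording is a separate question and does not show the imputation rule to be wrong.

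**Conclusion.** The concern does not hold. Section 8.1 fixes a complete and reproducible earliest-date convention, bounded by last dose and consistent with Table 2, whose purpose is to keep scans made under new therapy out of PFS and DOR. It can lose a true event: under the assumed gaps, in 74% of day-missing records when therapy followed progression by 7 days, 51% at 14, 28% at 21, 5% at 28 and none from 30 days, and in 98% to 88% of year-only records from 7 to 42 days. These shares apply only to records with a partial date, progression at least two days after last dose and therapy truly later. The SAP gives no frequency for any of these conditions.

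The alternative has nearly the same error in the opposite direction, with break-even close to one half on equal windows, so it is a trade-off and not a demonstrated improvement. The consequence is limited to descriptive estimates of DOR, a secondary endpoint, and of PFS, which section 5.4.3 places under other efficacy analyses. ORR does not use Table 2, and section 5.3.3 plans no statistical comparison.

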8.2 Efficacy Data Handling

Handling of missing data for tumor assessment result

For the calculation of ORR, DCR and CBR, subjects with missing response status (subjects who do not have adequate postbaseline tumor assessments result) will not be included in numerator, but included in denominator.

Data of tumor assessment result after documented PD or discontinuation from treatment

For the analysis of tumor assessment relevant efficacy endpoints, tumor assessment results after PD or last observation visit (for non-PD subjects) are excluded from the analyses, but included in subject data listing.

8.3 Safety Data Handling

Adverse Events

AEs with incomplete start dates will be considered treatment emergent if:

- Day and month are missing and the year is equal to or after the year of the first dose date
- Day is missing, and the year is after the year of the first dose
- Day is missing and the year is equal to the year of the first dose date and the month is equal to or after the month of the first dose date
- Year is missing, or
- Complete date is missing

Concomitant Medications

Medications will be considered concomitant if:

- Day and month are missing and the year is equal to or after the year of the first dose date
- Day is missing, and the year is after the year of the first dose
- Day is missing and the year is equal to the year of the first dose date and the month is equal to or after the month of the first dose date or
- Year is missing, or
- Complete date is missing

Visit and Analysis Windows

The visit recorded in CRF will be used for safety summary by visit. The purpose of visit windows for safety analyses is to provide a single record per subject per visit for the calculation of descriptive summary statistics for safety parameters (eg, laboratory values and vital signs, etc.), and change from baseline by visit, if a same visit has 2 or more observations. The observation closest to the target date will be used in by visit summaries. If 2 or more observations have the same distance to the target visit day, the one that has the highest CTCAE grade or is furthest away from the normal range and the earliest observation will be used.

Other safety analyses (eg, worst postbaseline grade in laboratory results) will include all observations within 30 days after the final dose of study treatment.

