5.2.5 Prior and Concomitant Therapy

All investigator terms for medications recorded in the CRF will be coded to an 11-digit code using the World Health Organization Drug Dictionary (WHO DD). The number (percentage) of subjects who took prior and concomitant medications will be summarized on the Efficacy Analysis Set for each dose level/tumor cohort, and for phase/overall (as needed) by Anatomical Therapeutic Chemical class 1, pharmacologic class 3, and WHO DD preferred term (PT). Prior medications are defined as medications that started before the first dose of study drug regardless if they were either stopped before the first dose of study drug or continued during the study. Concomitant medications are defined as medications that (1) started before the first dose of study drug and were continuing at the time of the first dose of study drug, or (2) started on or after the date of the first dose of study drug up to 30 days after the subject's last dose. Medications received after 30 days of last dose will be considered as post-treatment medications. The summary will be presented for each dose level/tumor cohort, and for phase/overall (as needed). A medication that cannot be determined as prior/concomitant/post treatment due to missing/incomplete dates will be regarded as a concomitant medication. All medications will be presented in subject data listings.

Any anticancer therapies (medication, procedure) received during survival follow-up and any palliative radiotherapy will also be summarized on the Efficacy Analysis Set.

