5.6.2.2 Adverse Events

The AE verbatim descriptions (investigator terms from the CRF) will be classified into standardized medical terminology using the Medical Dictionary for Regulatory Activities (MedDRA). AEs will be coded to the MedDRA lower level term (LLT) closest to the verbatim term. The linked MedDRA PT and primary system organ class (SOC) will also be captured in the database. The Common Terminology Criteria for Adverse Events ([CTCAE](#)) version 5.0 will be used to assess the severity of AEs.

A TEAE is defined as an AE that emerges during treatment (on or after the first dose date of study drug up to 30 days after the subject's last dose), having been absent at pretreatment (Baseline) or:

- Reemerges during treatment or up to 30 days following last dose of study drug, having been present at pretreatment (Baseline) but stopped before treatment, or
- Worsens in severity during treatment or up to 30 days following last dose of study drug relative to the pretreatment state, when the AE is continuous

The SAE is also counted as a TEAE if it emerges up to 90 days after the subject's last dose of study drug, or up to 30 days following cessation of study drug if the subject initiated new anticancer therapy, whichever is earlier.

Only those AEs that are treatment-emergent will be included in summary tables. All AEs, treatment emergent or otherwise, will be presented in subject data listings.

The incidence of TEAEs will be reported as the number (percentage) of subjects with TEAEs by SOC and PT. A subject will be counted only once within an SOC and PT, even if the subject experienced more than 1 TEAE within a specific SOC and PT. The number (percentage) of subjects with TEAEs will also be summarized by highest CTCAE grade.

An overview table, including the number (percentage) of subjects with TEAEs, TEAEs with CTCAE Grade 3 or above, treatment-emergent serious adverse events (SAEs), deaths, TEAEs leading to discontinuation from study drug, TEAEs leading to dose reduction, TEAEs leading to dose interruption, and TEAEs leading to dose reduction or interruption will be provided. Additionally, the TEAE by SOC and PT (any grade and grade ≥ 3 , maximum grade 3, 4 and 5), TEAE by decreasing frequency of PT (any grade and grade ≥ 3 , maximum grade 3, 4 and 5) will be summarized.

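### The partial-date rules in SAP 8.3 look only at first dose, so AEs known to lie outside the window in 5.6.2.2 are classed as treatment emergent, and the medication list conflicts with 5.2.5 in the same way

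*SAP*

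**What the plan says.** **Definitions.** SAP 5.6.2.2 places a TEAE "on or after the first dose date of study drug up to 30 days after the subject's last dose". It extends this for serious events: "The SAE is also counted as a TEAE if it emerges up to 90 days after the subject's last dose of study drug", cut to 30 days after cessation if new anticancer therapy was started, whichever is earlier. The flag decides what is tabulated: "Only those AEs that are treatment-emergent will be included in summary tables".

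For medications, SAP 5.2.5 counts as concomitant those that "started before the first dose of study drug and were continuing at the time of the first dose of study drug", and those started from first dose up to 30 days after last dose. Beyond that, "Medications received after 30 days of last dose will be considered as post-treatment medications". It has its own fallback: "A medication that cannot be determined as prior/concomitant/post treatment due to missing/incomplete dates will be regarded as a concomitant medication".

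**Partial-date rules.** SAP 8.3 opens the AE list with "AEs with incomplete start dates will be considered treatment emergent if" and gives five alternatives. Three compare the known year, or year and month, with those of first dose; "Day is missing, and the year is after the year of the first dose" is one. The other two accept a missing year or a wholly missing date outright. The medication list repeats the same five conditions without saying whether the start or the stop date is tested. Neither list mentions the last dose or a stop date.

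**The concern.** A default towards treatment emergent is sensible when the timing is unknown. Here the rule also fires when the known part of the date already settles the matter the other way. An event dated only to a month well past the end of the window, or one that had stopped before first dose, is a TEAE under 8.3 and is not one under 5.6.2.2. The two sections give different answers for the same record, and a programmer could follow either.

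What is at stake is the content of the TEAE tables. Safety and tolerability are a primary objective of the Phase 1b part and a secondary objective of both parts, and the cohorts are small enough for one subject to be visible in a rate. For medications, the same record can be concomitant under 8.3 and post-treatment under 5.2.5.

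**Working it through.** The plan gives no figure to reproduce. The check applies the 8.3 conditions literally and asks whether any calendar date consistent with the known parts could fall in the window.

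**Inputs.** The windows are first dose to last dose + 30 days (AEs in general) and to last dose + 90 days (SAEs without new anticancer therapy), both from 5.6.2.2. The dates are assumed for illustration: first dose 15 March 2021, last dose 10 September 2021. The windows then end on 10 October 2021 (+30) and 9 December 2021 (+90).

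| Case | Known start | Known stop | 8.3 | 30-day window | 90-day window |
|---|---|---|---|---|---|
| A | Nov 2021 | none | TEAE | impossible | possible |
| B | Jun 2022 | none | TEAE | impossible | impossible |
| C | 2022 | none | TEAE | impossible | impossible |
| D | Mar 2021 | 10 Mar 2021 | TEAE | impossible | impossible |
| E | 2021 | 1 Feb 2021 | TEAE | impossible | impossible |
| F | missing | 1 May 2019 | TEAE | impossible | impossible |

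B and C fail for want of an upper bound, whether or not the event is serious. D, E and F fail for want of a stop-date check. A is wrong for a non-serious AE. For an SAE it is wrong only if new anticancer therapy had started, which cuts the limit to 30 days.

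**Reach of the rule.** Take the 36 calendar months from March 2021 to February 2024, with the day missing in each. 8.3 flags all 36.

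- Wholly beyond 10 October 2021: November 2021 to February 2024 = 2 + 12 + 12 + 2 = 28 months.
- Wholly beyond 9 December 2021: January 2022 to February 2024 = 12 + 12 + 2 = 26 months.

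These counts show that the rule is open-ended. They do not estimate how often such records occur.

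**Medications.** If the list tests the start date, as the AE list does, then A, B and C are concomitant under 8.3 but post-treatment under 5.2.5, and D, E and F are concomitant under 8.3 although they were not continuing at first dose. If the list tests the stop date, the D to F problem largely falls away, but the missing upper bound remains.

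**Effect on a rate.** 5.6.2.2 counts a subject once per preferred term. One misclassified subject adds 100/n points if there is no other TEAE under that term, and otherwise adds nothing:

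- n = 15 (the number per tumor cohort at the interim futility review in SAP section 6): 100/15 = 6.7 points
- n = 30 (assumed): 100/30 = 3.3 points
- n = 40 (assumed): 100/40 = 2.5 points

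**The case against.** **The rule is conservative, and all AEs are listed.** Over-inclusion is the safer direction, and a reader can find any such record in the listings. That is true, but a conservative default belongs where timing is unknown. Here the timing is known well enough, and the rule overrides the SAP's own definition. Listings do not correct the tables.

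**5.2.5 already deals with medications.** Its fallback applies only where the class cannot be determined, so 8.3 could be read as working inside it. This is fair and narrows the medication half to a conflict of wording. 8.3 does not state that limit, however, and its conditions take in drugs that can be classified.

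**Collection periods and programming documents are not shown.** If collection stops near the end of the window, late non-serious records will be few. This bears on the size of the effect and leaves the contradiction in place. SAP section 9 puts derivation rules in separate documents, but those should carry out the SAP and not silently correct it.

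**Stronger readings that the document does not support.**

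- A reader might infer that every AE known to start more than 30 days after last dose is misclassified. Suppose the last dose is on 10 January 2023 and onset is recorded as March 2023. Onset is then 50 to 80 days after last dose. This is outside the window for a non-serious AE, but inside it for an SAE with no new anticancer therapy.
- A reader might infer that later anticancer drugs swell the concomitant tables. Section 5.2.5 summarizes anticancer therapy in survival follow-up separately, and 8.1 has its own partial-date rule for it, tied to the last dosing date.
- A reader might infer that the DLT results are affected. They are reported on the DLT Analysis Set, and nothing routes them through this rule.
- Nothing in the SAP shows what such late events would be due to.

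**Conclusion.** The contradiction holds on the text. For AEs, 8.3 gives a classification that 5.6.2.2 rules out in three situations: a non-serious AE whose known month or year lies wholly beyond 30 days after last dose, an SAE wholly beyond its own limit, and an AE with a complete stop date before first dose. For medications, the missing upper bound conflicts with 5.2.5 whichever date is tested. The stop-date part depends on reading the list as a test of the start date.

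The error runs one way, towards over-counting. The 100/n figures are a maximum per misclassified subject, the cohort sizes of 30 and 40 are assumptions, and the SAP gives neither the number of partial dates nor the length of AE collection. The effect is probably small. It should still be corrected, because a stated rule gives a wrong answer and the remedy is cheap.

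**What to change.** In SAP 8.3, apply the treatment-emergent or concomitant default only when the known date parts cannot decide. Add to both lists:

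*unless the earliest date consistent with the known start-date parts is after the end of the applicable window in 5.6.2.2 (by AE seriousness) or 5.2.5, or the latest date consistent with the known stop-date parts is before the first dose date.*

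Also state that:

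- the medication list tests the start date, and a drug started before first dose and still continuing then remains concomitant under 5.2.5;
- the default is kept when the end of the window itself cannot be determined because the start date of new anticancer therapy is missing.

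Under this wording cases B to F are excluded. Case A is excluded for non-serious AEs and for medications, and is kept for an SAE unless new anticancer therapy had started.

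The cost is a few sentences in the SAP and a modest programming change. The SAE limit needs the start date of new anticancer therapy, so the derivation must draw on that field and on the imputation rule for it in 8.1.
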